#### 8.6.2.3. Tumor Markers

CA-125 and WT1 by RT-PCR will be summarized for only ovarian cancer and AML patients, respectively. Additional tumor markers may be identified and summarized as appropriate.

To evaluate the response according to CA-125, the definition of response described in Rustin, et al. [Rustin-2011] will be used. A response according to CA-125 has occurred if there is at least a 50% reduction in CA-125 levels from baseline sample. This response must be confirmed at least 28 days later by a repeat assessment that is a at least a 50% reduction or is within 10% ( $\pm$  10%) using the same assay method. Additionally, the baseline must be at least 2 times the upper limit of normal and drawn within 4 weeks prior to first dose date. Progression is defined as an increase of 2 times the nadir value at any time. If the nadir is less than the upper limit of normal then a progression will be declared at 2 times the upper limit of normal. This must be confirmed at least one week

later. Not-response/Non-PD will be assessed if neither the criteria of response or progression are achieved. A table will present the number and percentage of patients for their best response (response>Not-response/Non-PD>progression) for the CA-125 population. Additionally, the percent change from baseline may be presented over time graphically.

The descriptive statistics for the log transformed RT-PCR value will be presented for bone marrow and blood separately by each assessment and by different cohort. For any assessment, if there are multiple assessments within each category (either bone marrow or blood), choose the highest one. If the result of RT-PCR is undetectable, impute it as half of  $5.0 \times 10 \text{ copy}/\mu g$  RNA. The percent change from baseline will be presented over time graphically for WT1 by RT-PCR for the log transformed RT-PCT values.

Additionally, other markers identified upon review may be summarized and/or categorized according to standard criteria.

A by-patient listing for both CA-125, WT1 by RT-PCR, and other tumor markers identified will be provided separately.

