# 4.3. Determination of Sample Size

The total sample size for the study will be determined by the number of patients treated in each dose cohort and the number of dose cohorts necessary to determine the MTD.

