## 8.3. Analysis Populations

There are 3 planned analysis populations.

- Safety population: includes all enrolled patients who receive at least 1 dose of study drug and will be used for the analysis of all safety and efficacy data except as noted below
- DLT population: includes all patients in the Safety population who experience a DLT within the DLT evaluation period or completed the DLT evaluation without experiencing a DLT and will be used for analysis of DLT.
- Efficacy population: include all patients in the Safety population who are evaluable for response (for each irRC, IWG, CA-125 and WT1 by RT-PCR)
  - o Population for irRC response: including all the patients in the Safety population who are not AML patients and whose lesions are measureable and have at least one posttreatment assessment. (Note that any posttreatment irRC assessment is based on the baseline assessment)
  - O Population for modified IWG response: includes all the AML patients in the Safety population who have >5% marrow blasts or >50 copy/μ g RNA of quantitative RT-PCR for WT1 transcript before the first date/time of study drug and who have at least one posttreatment assessment.
  - o Population for CA-125 tumor marker: including all ovarian cancer patients in the Safety population who have a baseline CA-125 assessment and at least one assessment posttreatment.
  - Population for WT1 by RT-PCR tumor marker: includes AML patients in the Safety population who have a baseline assessment and at least one assessment posttreatment.
- Population for CTL: including all patients in the Safety population who has a baseline assessment of percentages of WT1-positive cells among CD8-positive cells and at least one post-baseline assessment

Additional populations for analyses of other tumor markers identified may be defined in a similar manner.

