- Unconfirmed irPD = Any irPD record after study day 1 and no record of irPD confirmed 4 weeks after, which include the situation that the PI can discontinue a patient from the study for the reason of PD without confirmation of PD after 4 weeks if patients have rapid symptomatic progression accompanied by a decline in performance status.

The assessment made by the investigator will be used for all summaries.

Best response is defined to be the best irRC response (irCR > irPR > irSD > irPD) evaluated after dosing until treatment discontinuation. Patients without post-baseline evaluations will be considered as unevaluable. Additional categories are defined for response (irCR + irPR) and disease control (irCR + irPR + irSD).

Tables will summarize the number and percentage of the best overall tumor response for each category by dose cohort, the number, percentage, and Wilson Score 95% CI will also be presented for the response categories of irCR, response, and disease control.

The percent change in tumor burden from baseline will be presented at each posttreatment tumor assessment graphically and in patient data listings. Percent change will be calculated as 100\*[(current tumor burden - baseline tumor burden)/baseline tumor burden]. The best change, i.e., the minimum of percent change from baseline for each patient will be displayed in a waterfall plot.

A by-patient listing of irRC assessment will be provided.

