## 8.6.3.2. Immune Response

Peripheral blood samples will be obtained for evaluation of WT1 peptide-specific CTL induction activity by tetramer assay and WT1 serum antibody titer by enzyme-linked immunosorbent assay (ELISA), and for isolation of PBMCs. In addition, blood samples will be obtained and blood serum archived for possible analyses of other biomarkers, such as protein and microRNA, that may be important to the understanding of WT2725 but which have not yet been selected. These results may be presented in figures and/or patient data listings.

For DTH assessments, the number of patients who have an injection with WT2725 and control will be displayed before and after injection for each dose. The number and percentage for the reaction of positive and negative based on the number of patients who have injections may also be presented for the WT2725 versus negative control. The summary for all the dose will also be generated. The patients who have at least one injection will be present. The number of positive reaction for overall is counted for the patients who have at least one positive reaction during all the doses. The number of negative reaction for overall is counted for those patients who have all negative reaction during all the doses. The corresponding percentage will also be displayed similary for each dose. The results may also be presented in data listings.

For WT1 by RT-PCR tumor marker, the descriptive statistics have been provided for the baseline, at each post-baseline assessment and change from baseline by dose cohort, including the minimum and maximum of all the post-baseline assessments.

Immunohistochemistry in tumor tissue may be evaluated by expression of CD8+, Foxp3, HLA class I, and other measurements using tumor tissue samples obtained before the first dose. Due to the sparsity of the post-baseline data, post-baseline results will only be listed but not summarized. Continuous results will be summarized in a table with mean, standard deviation, median, quartiles, minimum, and maximum. Categorical variables will be summarized in a table with frequencies and percentages. Additionally, histograms of continuous results and bar plots of categorical results will be presented.

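### The WT1 RT-PCR figure plots percent change of log values, so equal fold changes appear as different percentages depending on the baseline level

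*SAP*

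**What the plan says.** SAP Section 8.6.2.3 handles WT1 transcript on the log scale: "The descriptive statistics for the log transformed RT-PCR value will be presented for bone marrow and blood separately by each assessment and by different cohort". The base of the logarithm is not given. For results below detection it says "If the result of RT-PCR is undetectable, impute it as half of" 5.0 × 10 copies per µg RNA, which is 25. It then specifies the figure: "The percent change from baseline will be presented over time graphically for WT1 by RT-PCR for the log transformed RT-PCT values".

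The SAP gives one explicit percent-change formula, in Section 8.6.2.1 for tumor burden ("Percent change will be calculated as" 100 times current minus baseline, divided by baseline). No separate formula is given for WT1.

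The population for this marker (Section 8.3) "includes AML patients in the Safety population who have a baseline assessment and at least one assessment posttreatment". It sets no minimum baseline level, so a patient with an undetectable baseline can enter at the imputed 25.

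Section 8.6.3.2 adds a WT1 table in which "the descriptive statistics have been provided for the baseline, at each post-baseline assessment and change from baseline by dose cohort". That change is not a percentage, and its scale is not stated. Nothing elsewhere in the SAP replaces the percent-change figure.

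**The concern.** Percent change is meaningful on a scale with a true zero, such as tumor burden or copy number. A log copy number has no true zero: its zero is 1 copy per µg, a point fixed only by the choice of unit. Dividing a log change by the log baseline therefore divides by an arbitrary quantity. For the same biological change, a low-baseline patient plots further from zero than a high-baseline patient.

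WT1 by RT-PCR is the AML tumor marker under the secondary objective on antitumor response (Sections 3.2 and 8.6.2.3). AML groups are small: Part 2 plans about 10 patients per dose level, with at least 4 having AML (Section 4.1). Chance differences in baseline between such groups could look like differences between doses. The same section also allows a percent-change plot for CA-125 with no log transformation mentioned, so a reader may take the two percentages to mean the same thing.

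**Working it through.** The plan states no figure to reproduce; the check is algebra plus examples.

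**Inputs**
- Plotted quantity: percent change from baseline of log values (SAP 8.6.2.3).
- Formula: 100 × (current - baseline) / baseline, borrowed from SAP 8.6.2.1.
- Imputed undetectable value: 0.5 × 50 = 25 copies/µg, with log10(25) = 1.398 (SAP 8.6.2.3).
- Detection limit: not stated. I take it as 50, because the imputation rule implies it; Section 8.3 also uses a threshold above 50 copies/µg for the IWG population.
- Baseline range: not in the documents. I assume values up to 10^6 copies/µg.

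**Step 1: algebra.** With baseline b and fold change f,

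100 × [log(f·b) - log(b)] / log(b) = 100 × log(f) / log(b).

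For fixed f the result depends only on b. The log base cancels, so log10 and natural log give the same percentage. The unit does not cancel: a 10-fold fall from 100,000 copies/µg gives -1/5 = -20%, but the same result expressed per ng (baseline 100) gives -1/2 = -50%.

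**Step 2: falls that end at or above 50 copies/µg**

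| Change | Baseline | Calculation | Plotted |
|---|---|---|---|
| 10-fold fall (-90%) | 500 | -1/2.699 | -37.1% |
| 10-fold fall | 1,000 | -1/3 | -33.3% |
| 10-fold fall | 10,000 | -1/4 | -25.0% |
| 10-fold fall | 10^6 | -1/6 | -16.7% |
| 100-fold fall (-99%) | 5,000 | -2/3.699 | -54.1% |
| 100-fold fall | 10^6 | -2/6 | -33.3% |

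The spread is 37.1/16.7 = 2.2 for a 10-fold fall and 54.1/33.3 = 1.6 for a 100-fold fall. A 90% fall from 1,000 and a 99% fall from 10^6 plot at the same height.

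**Step 3: rises.** A 10-fold rise from the imputed 25 plots as 1/1.398 = +71.5%. From 10^6 it plots as 1/6 = +16.7%.

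**Step 4: reading the figure backwards.** A plotted -20% means a fall by a factor of b^0.2: 4.0-fold from 1,000, 6.3-fold from 10,000 and 10-fold from 100,000.

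**Step 5: what is preserved.** The lowest value the rule produces is 25, so log(b) is positive and the sign is always right. Within one patient log(b) is a constant, so the curve is the log change rescaled, with its shape and order over time intact.

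**Step 6: the alternative.** Change in log10 copies is -1.0 for a 10-fold fall and +1.0 for a 10-fold rise at every baseline, and it does not depend on the unit.

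**The case against.** The strongest reply is that little rests on this figure. It is one descriptive plot in the AML subset of an open-label Phase 1 study without a powered sample size (Section 4.3: "The total sample size for the study will be determined by the number of patients treated in each dose cohort" and the number of cohorts needed). No test, response category, MTD rule or stopping rule uses the plotted percentage. The SAP also provides log-value summaries by assessment and cohort, a by-patient listing, and the change-from-baseline table in Section 8.6.3.2. All of this stands and limits the severity. It does not correct the figure, and the table is only a partial remedy because its scale is unstated.

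A second reply is that the sentence is loose wording for a plot of log change, or of raw percent change. That is possible, but a programmer following it literally produces the plot described here, so the sentence needs correcting either way.

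Three stronger readings are tempting and are not supported:
- A reader might infer that a 100-fold fall from 1,000 plots as -67%. That fall ends at 10 copies. If 50 is the detection limit, the SAP would impute 25, and the plotted value is 100 × (1.398/3 - 1) = -53.4%.
- A reader might infer a roughly four-fold distortion over the assay's range (71.5/16.7 = 4.3). That ratio arises only for a rise from an imputed baseline set against an assumed 10^6. The documents give no upper assay limit, and for falls above the floor the spread is about two-fold.
- A reader might infer that the figure orders patients by baseline instead of by effect. The numerator is still the log fold change, so the two are mixed and neither replaces the other. The SAP plans no ranking of patients on this marker; the waterfall plot is for tumor burden.

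**Conclusion.** The point holds and is minor. As written, the figure shows 100 × log(fold change) / log(baseline), which is not a comparable measure of WT1 change between patients or cohorts. The algebra needs no assumption beyond applying the usual percent-change formula to the logs. The sizes rest on assumed baselines up to 10^6 copies/µg and a detection limit of 50: a 10-fold fall plots between about -37% and -17%, a 100-fold fall between about -54% and -33%, and a 10-fold rise at +72% from the imputed 25 against +17% from 10^6. Different baselines would change these figures but not the defect. The documents do not support a claim that any conclusion on response, dose or safety would be altered.

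**What to change.** In Section 8.6.2.3, replace the percent-change figure with change from baseline in log10 copies per µg RNA (the log10 ratio to baseline), and state the log base. State the same scale for the WT1 change-from-baseline summary in Section 8.6.3.2.

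Percent change of untransformed copies would also be free of the baseline effect, but it is a weaker choice: falls are squeezed against -100% (99% and 99.9% are hard to tell apart), while a 100-fold rise plots as +9,900%.

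The cost is one sentence in Section 8.6.2.3, a clarifying phrase in Section 8.6.3.2 and one figure program. The log values are already being derived, so no new data are needed.

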## 8.6.3. Exploratory Analyses

The Population for Biomarkers includes all patients in the Safety population who have the Day 29 biomarker assessment completed. All other exploratory analyses will use all patients in the Safety population of patients with the endpoint of interest measured at baseline and at least once posttreatment.

Biomarker sample collection will be conducted as indicated on the Schedules of Assessment (Table 1 and 2). Tables may summarize the statistics at the screening assessment, at each posttreatment visit, and at the end of study.

A table will summarize the Spearman rank correlation and 95% CI between the level of expression of WT1 protein and the degree of the immune response by dose cohort at each visit as measured by CTL induction. Additionally, the correlation at each visit may be presented graphically.

Scatter plots of maximum (mean, median) post-baseline values of immune response measured by CTL induction versus maximum (mean, median) post-baseline values of CA-125 will be presented. Additionally, scatter plots of maximum (mean, median) post-baseline values of immune response measured by CTL induction versus maximum (mean, median post-baseline values of WT1 by RT-PCR will be presented.

A listings of level of expression of WT1 protein will be provided.

If additional reports are provided by the biomarker vendor(s) then additional analyses may be performed and the vendor's report will be an appendix to the clinical study report.

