#### 4. STUDY DESIGN

# 4.1. General Description

This is a Phase 1, open-label, dose-escalation, 2-part study in adult patients with advanced malignancies known to overexpress the WT1 protein. The study will primarily evaluate DLT and define the MTD of WT2725 Dosing Emulsion during the DLT Evaluation Period, which extends from the day of the first dose of study drug to just prior to the fifth dose (Days 1 - 29). In addition, antitumor activity and biomarkers indicative of immune response will be evaluated from the first dose until discontinuation of the patient from the study. An end of study assessment will take place within 28 days after the last dose of study drug and prior to the start of alternate antineoplastic therapy.

The initial patients in each dose escalation cohort will be enrolled at least one week apart to evaluate initial safety from the first 2 patients, then a "rolling-six" design will be employed that allows accrual of 2 to 6 patients concurrently in each dose escalation cohort.

In Part 1 of the study, the 0.3 mg cohort will be conducted first. After safety and tolerability have been established for the first cohort, enrollment of subsequent patients will be conducted sequentially in subsequent cohorts and continue until the MTD or all planned cohorts are attained. Enrollment of each cohort may include patients with any of the eligible tumor types (see below). Enrollment of the highest tolerable dose cohort (MTD or highest planned cohort) will continue until there are at least 6 patients total in the study with each tumor type that are evaluable for DLT, biomarkers, and response. This dose is considered the recommended phase 2 dose (RP2D). Enrollment of up to 3 RP2D cohorts of 10 patients each of a specific tumor type may take place at this dose in order to further characterize the safety and efficacy of WT2725 Dosing Emulsion at this

dose in these subsets of patients. Additional dose escalation cohorts after the initial expansion cohorts may be enrolled if a MTD has not been determined and significant signs of toxicity have not been observed in the expansion cohorts.

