In Part 2 of the study, the 18.0 mg cohort will be conducted first. After safety and tolerability have been established for the 18.0 mg cohort, enrollment of subsequent patients will be conducted sequentially in the 27.0 mg cohort. Approximately 10 patients at each dose level (18.0 and 27.0 mg) with at least 4 patients with each malignancy type (glioblastoma and acute myeloid leukemia [AML]) will be enrolled at each of these dose levels. If the MTD is reached in Part 2 before the total of 20 patients are enrolled, remaining patients will be enrolled at the prior dose level. In the event that a dose level is excluded from further study due to dose limiting toxicity all patients may continue the study at the most recently completed dose without DLT, eg, if the 27.0 mg dose is excluded due to DLT all patients may continue at 18.0 mg.

Patients who have completed the consolidation phase of their assigned cohort and have not experienced a DLT,  $\geq$  Grade 2 study drug-related injection-site reaction, or required a dose reduction may have their dose escalated to that of the highest cohort for which safety and tolerability have been established. The expected time to enroll each dose escalation cohort (2 - 6 patients) is between 6 and 12 weeks.

Each part of the study will include 3 treatment phases based on intended timing of study drug dosing as indicated below (see Figures 1 and 2):

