Again, in subsequent dose escalation cohorts in Part 1, if 3 patients in a dose cohort complete the DLT Evaluation Period and there are no DLTs identified, then the dose level is increased, otherwise enrollment of additional patients (up to 3 more) may be permitted in the same cohort. If one of 3 patients in a dose escalation cohort experiences a DLT then up to a total of 6 patients are enrolled in the same dose cohort and dose escalation may only proceed if no additional patients experience DLT. Patients not evaluable for DLT assessment may be replaced.

In Part 2 of the study, the 18.0 mg cohort will be conducted first. If 3 patients in the dose cohort complete the DLT Evaluation Period and there are no DLTs identified, then the 27 mg dose cohort may begin, otherwise enrollment of additional patients (up to 3 more) may be permitted in the same cohort. If one of 3 patients in a dose escalation cohort experiences a DLT then up to a total of 6 patients are enrolled in the same dose cohort and dose escalation may only proceed if no additional patients experience DLT. After safety and tolerability have been established for the 18.0 mg cohort, enrollment of subsequent patients will be conducted sequentially in the 27.0 mg cohort. If additional patients are ready to enroll in the study prior to completion of the DLT Evaluation Period for the 27.0 mg dose cohort, up to a total of 10 patients may be enrolled at the 18.0 mg dose level. Approximately 10 subjects at each dose level (18.0 and 27.0 mg) with at least 4 patients with each malignancy type (glioblastoma and AML) will be enrolled. If the MTD is reached in Part 2 before the total of 20 patients are enrolled, remaining patients will be enrolled at the prior dose level. Patients not evaluable for DLT assessment may be replaced.

If at any time during dose escalation 2 or more patients experience DLT within a dose cohort that suggests that the MTD has been exceeded; no additional patients will be enrolled into that dose cohort and dose escalation will end. The MTD will be the dose level below that which resulted in 2 or more patients experiencing a DLT. If the suspected MTD is based on a cohort in which fewer than 6 patients were enrolled then additional patients will be enrolled and treated at that dose level until there is a total of 6 patients evaluable for DLT within that dose escalation cohort.

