<sup>d Includes systolic and diastolic blood pressures, pulse, respirations rate, and oral body temperature.

e If HLA typing has been performed previously, these results may be used, otherwise HLA typing should be the first procedure performed during screening.

<sup>f For females of child-bearing potential.

g Includes hepatitis B and C, human immunodeficiency virus (HIV)-1, and HIV-2, if there are signs or symptoms suggestive of infection.

<sup>h See Appendix IV of protocol for list of required laboratory tests at each visit.

Assessment may be omitted if an assessment was performed within the previous 3 days. If there are multiple assessments the most recent ones should be used.

<sup>1 Perform DTH skin test injections approximately 48 hours (but no sooner than 24 hours) prior to the evaluation.

- k Perform DTH skin test injections immediately before administration of study drug.
- 1 If the DTH reactivity results in erythema with induration greater than 2 cm, or leads to ulceration of the skin test site, further DTH testing should not be conducted for the patient.
- m Evaluation should be made on the planned dosing day, prior to study drug administration.
- n Evaluation should be approximately 48 hours (but no sooner than 24 hours) after the DTH skin test injection.
- o Samples obtained 6 hours (± 30 minutes) and 48 hours (± 6 hours) postdose.
- p In place of tumor tissue samples from a biopsy during screening, archived tumor tissue samples may be provided. Availability of tumor tissue samples should be determined during screening through provision of the accession number or other identification number. If necessary, the tumor tissue sample biopsy should be performed after study eligibility has been confirmed and before the first dose of study drug. The tumor tissue samples will only be provided to the sponsor for subjects who receive study drug. In place of archival tumor tissue samples, subjects with AML should have available a bone marrow aspirate and/or bone marrow biopsy with PCR for WT1 transcript performed before the first dose of study drug. Patients with AML should also have peripheral blood assessed for blasts and WT1 transcript.
- q IHC need not be performed for patients with AML provided RT-PCR for WT1 transcript is assessed.

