# 8. STATISTICAL ANALYSIS

In this section and all after, when tables are presented by posttreatment visits, the last visit will be the visit at the end of study. When applicable, visits after the start of the maintenance phase and unscheduled visits will be included in a summary of maximum and minimum values observed for each patient's posttreatment visits, i.e., the minimum and maximum values are based on all the post treatment visits.

In general descriptive statistics for continuous variables will be summarized by the mean, standard deviation, 25th percentile, median (50th percentile), 75th percentile, minimum and maximum values. When continuous variables are displayed for less than 3 patients, only the number of observations will be presented. Categorical variables will be summarized using counts and percentages.

All raw data will be presented to the original number of decimal places. The means and medians will be presented to 1 more decimal place than the raw data. The standard deviations will be presented to 2 more decimal places than the raw data.

Baseline will generally be defined as data obtained as the last non-missing value prior to the first dose of study drug, i.e., including the pre-dose assessment on Day 1, assessments during screening and other assessments prior to the first dose of study drug.

AE tables and laboratory tables will be presented by visits and by tumor group. Tumor groups are defined as groups of overall, solid tumor, and AML patients.

Unless otherwise stated, summaries will be produced by dose cohort, which is defined as the intended and starting dose to which the patient was enrolled.

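### The WT1-protein versus CTL correlation is planned only within dose cohort at each visit, with no overall estimate, and in most cohorts its 95% CI would be uninformative

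*SAP*

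**What the plan says.** SAP 8.6.3 specifies a table of the "Spearman rank correlation and 95% CI between the level of expression of WT1 protein" in tumor cells and a CTL measure. The CTL side of the correlation, together with the level at which it is tabulated, is worded as "the degree of the immune response by dose cohort at each visit as measured by CTL induction". The section adds that the correlation at each visit may be graphed, without saying whether the graph pools cohorts. No overall or dose-adjusted row is named.

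SAP 8 states that "summaries will be produced by dose cohort, which is defined as the intended and starting dose to which the patient was enrolled", so RP2D expansion patients count in the cohort of their starting dose.

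Cohort sizes come from SAP 4.1 and 4.1.1:

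- The design "allows accrual of 2 to 6 patients concurrently in each dose escalation cohort", and Part 1 may escalate "if 3 patients in a dose cohort complete the DLT Evaluation Period and there are no DLTs identified".
- "Enrollment of up to 3 RP2D cohorts of 10 patients each of a specific tumor type may take place at this dose", meaning the Part 1 RP2D.
- Part 2 plans for "Approximately 10 patients at each dose level (18.0 and 27.0 mg) with at least 4 patients with each malignancy type"; the two types are AML and glioblastoma.

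On who contributes WT1 protein data, the schedule footnotes in SAP 6.1 say "IHC need not be performed for patients with AML provided RT-PCR for WT1 transcript is assessed". SAP 8.6.3.2 only lists post-baseline IHC, so WT1 protein is in effect one baseline value per patient.

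**The concern.** The objective in SAP 3.3 asks whether immune response depends on WT1 protein expression. The endpoint in SAP 6.4 is that correlation at each assessment time. Neither mentions dose, yet the only planned numerical analysis divides the patients by dose cohort before correlating.

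Nearby analyses are not restricted in this way. The Wilcoxon tests on CTL (SAP 8.6.3.1) are done within each cohort and across all cohorts, and the IWG summaries (SAP 8.6.2.2) are also given overall. The missing overall row therefore looks like an omission rather than a choice.

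At stake is whether the report contains one usable estimate of the association, or mainly a grid of intervals spanning most of the range from -1 to 1. With no overall estimate and no chosen visit or CTL summary, a reader would also tend to pick out whichever cell looks striking.

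**Working it through.** The documents give no sample size, power or precision target for this correlation (SAP 4.3 ties the total only to cohort sizes and the MTD), so there is no planned figure to reproduce.

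**Head count by cohort, before dropout**

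- 0.3, 0.9 and 3.0 mg: about 3 to 6 each.
- 9.0 mg: 3+30 = 33 to 6+30 = 36 with full RP2D expansion. If one RP2D cohort is AML without IHC, 23 to 26.
- 18.0 and 27.0 mg: about 10 each, at least 4 of each malignancy. If AML patients have no IHC, 4 to 6 each.
- Check: 4×3+30+20 = 62 and 4×6+30+20 = 74, inside the 60 to 80 of SAP 4.1.

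**Interval within one cohort at one visit**

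SAP 7.1 names the SAS CORR procedure but no interval method, so Fisher z is assumed. The half-width around zero is tanh(1.96/√(n−3)). This standard error is slightly optimistic for ranks. The smallest attainable p comes from the exact permutation distribution.

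| n | Half-width around 0 | Exact test |
|---|---|---|
| 3 | undefined (n−3 = 0) | smallest p 0.333 |
| 4 | 0.96 | smallest p 0.083 |
| 5 | 0.88 | p<0.05 only at perfect rank agreement or reversal (p 0.017) |
| 6 | 0.81 | needs an absolute correlation of at least 0.886 |
| 10 | 0.63 | not computed |
| 23 | 0.41 | not computed |
| 36 | 0.33 | not computed |

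At n=3 or 4 no data set can reach p<0.05. At n=3 a correlation of exactly ±1 arises by chance one time in three. For an assumed true correlation of 0.5, approximate power is 16% at n=6, 69% at n=23 and 88% at n=36.

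**Overall estimate adjusted for dose cohort**

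A partial Spearman correlation with five indicators for six cohorts has half-width tanh(1.96/√(N−3−5)) = tanh(1.96/√(N−8)).

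- Assumed N=30: tanh(1.96/√22) = 0.40.
- Assumed N=50: tanh(1.96/√42) = 0.29.
- Full expansion, AML without IHC in Part 2 and in at most one RP2D cohort: N = 3+3+3+23+4+4 = 40 to 6+6+6+36+6+6 = 66, giving 0.33 to 0.25.
- No RP2D expansion and six in every cohort (N=36): 0.35.

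Combining within-cohort Fisher z values costs more: Σ(n−3) replaces N−8, which gives 0.51 at N=30 and 0.33 at N=50 if every cohort has at least 3 patients.

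The correlation detectable with 80% power is tanh(2.80/√(N−8)): 0.54 at N=30 and 0.41 at N=50. At a true correlation of 0.3, power is Φ(0.3095×√22−1.96) = 31% at N=30 and Φ(0.3095×√42−1.96) = 52% at N=50.

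Adjusting also for three solid-tumor types (glioblastoma, ovarian and lung, per Protocol Amendment No. 1) uses two more degrees of freedom: tanh(1.96/√20) = 0.41 to tanh(1.96/√40) = 0.30.

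**The case against.** The strongest reply is that this is an exploratory variable under an objective classed as other, with no hypothesis or decision rule, and that per-visit reporting follows the endpoint in SAP 6.4. That stands. It limits the consequence and means the per-visit results should be kept. It does not explain the split by dose cohort, which the endpoint does not ask for. The optional graph might pool cohorts, but the SAP does not say so and the graph carries no stated interval.

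A reader might infer more than the documents support:

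- **That every cell holds 3 to 6 patients, so the plan cannot address its objective.** This fails at 9.0 mg. The Amendment No. 6 summary in the protocol records additional patients treated at that dose, although it gives no number.
- **That AML patients will have no WT1 protein data.** The footnote permits omitting IHC; it does not rule IHC out.
- **That about 3 intervals will exclude zero by chance.** The pre-maintenance grid has 4×8 + 2×14 = 60 cells, and 60×0.05 = 3. But some of those cells may have no defined interval, and at n=4 no exact test can reach 0.05. Results at successive visits in the same patients are also dependent.
- **That pooling settles the question.** Power is low for a correlation near 0.3. Tumor type is partly confounded with dose, because Part 2 takes only glioblastoma and AML.

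**Conclusion.** The concern holds in limited form. SAP 8.6.3 gives no overall estimate for a question that is not dose-specific. In up to five of the six cohorts the planned interval would be undefined or about ±0.81 to ±0.96. At 9.0 mg the interval may be usable (±0.41 to ±0.33), but it is still split over every visit with none designated, and it leaves the other cohorts unused.

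A dose-adjusted overall estimate, at about ±0.40 to ±0.29, would be far more precise than the small cohorts. Its gain over a fully expanded 9.0 mg cohort is modest.

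These figures assume Fisher z intervals, 30 to 50 patients with IHC, and cohort counts before dropout. SAP 8.6.3 requires a completed Day 29 assessment for the biomarker population and no dropout rate is stated, so actual intervals may be wider. The safety and MTD conclusions do not depend on this table.

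**What to change.** In SAP 8.6.3:

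1. Add an overall Spearman correlation with 95% CI at each visit, stratified for dose cohort (partial Spearman or within-cohort ranks), and name the interval method.
2. Add the same estimate for one prespecified CTL summary per patient, stating which visits enter it. It must be defined when baseline CTL is 0, a case SAP 8.6.3.1 provides for, so a log ratio to baseline would not serve. The mean post-baseline CTL already derived there, or a rank-based change from baseline, would.
3. Show tumor type in the plots or stratify for it.
4. Keep the cohort-by-visit results as descriptive, and suppress the CI below a stated n. SAP 8 already withholds descriptive statistics for fewer than 3 patients.

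The cost is SAP wording and one table; no new data are needed. The overall estimate assumes a similar association across doses and tumor types, which the plots can check.
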